9.3 Specific Tests and Evaluations

Donors

All live donors will provide written informed consent for participation in this trial. Donor characteristics (deceased or living, age, race, sex, medical history, laboratory tests, and ischemic time) will be documented. Live donors will be specifically informed of the experimental nature of their recipient's protocol. The living donor may decline to consent for the blood donation aspect of this protocol without affecting the recipient's ability to participate in this study. However if the donor declines to sign the informed consent for participation in all aspects of the protocol, the recipient may not be enrolled.

Recipient Evaluations Prior to Immunosuppressive Dosing

After informed consent is obtained, the following tests and evaluations are to be conducted within 72 hours prior to randomization/study treatment unless otherwise specified:

- Demographics
- Medical history
- Physical examination
- Vital signs
- Urinalysis

- Serum pregnancy test for females of childbearing potential
- CBC with differential
- Lymphocyte subsets, and baseline Ki67
- Peripheral blood transcription
- Donor specific MLR/ ICCS and antibody titers
- Blood chemistry: blood urea nitrogen (BUN), AST, ALT, total bilirubin, creatinine, sodium, potassium, calcium, bicarbonate, chloride, glucose
- HIV antibody, HBsAg, HCV Ab
- EBV and CMV IgG and IgM, and EBV and CMV PCR
- BK viremia and viruria
- Panel Reactive Antibody/ alloantibody assessment
- Donor characteristics including ischemic time

Evaluations During Treatment Period

See flowcharts in Section 8 for specific tests and the timing of test to be drawn during the study period. In addition, a general health related quality of life measure will be collected from all patients. We will utilize the SF-36 questionnaire. The instrument will be administered pre-transplant and at post-transplant visits in month 6, 12, 18, 24, then annually thereafter.

A neurologic assessment (exam and history) will be done every 3 months up to the year 2 annual visit. After year two, these assessments will be done every 6 months until the end of participation in the study.

The neurologic exam will include:

A review of any new neurological symptoms or changes, such as:

- Personality
- Memory
- Headaches
- Pain
- Seizures
- Impairment of consciousness
- Swallowing
- Vision, hearing, and language function
- Coordination
- Gait
- Weakness
- Sensory alterations
- Sphincter disturbances
- Involuntary movements

The neurologic exam will include testing of:

- Mental status
- Gait
- Speech
- Cranial nerves
- Cerebral function
- Deep tendon reflexes
- Sensory function
- Motor function

The patient will be watched closely for any neurological changes that may develop throughout the study. If the patient develops a new finding or if a condition worsens, there will be a follow-up neurologic exam. If needed, more tests and procedures might be ordered and the patient might be referred to a Neurology specialist.

10. INVESTIGATIONAL PRODUCTS

Investigational product is defined as a pharmaceutical form of an active ingredient or placebo being tested or used as a reference in the study, whether blinded or unblinded.

This trial will be conducted under an FDA Investigational New Drug application held by the Sponsor-investigator. All medications are approved for human use

10.1 Belatacept Preparation

A pharmacist or qualified personnel at the site will prepare the drug for i.v. administration.

Care must be taken to assure sterility of the prepared solution, as the drug product does NOT contain any antimicrobial preservatives or bacteriostatic agents.

All dilutions and transfers of Belatacept must be performed using polypropylene non-siliconized syringes (Norm-Ject®) manufactured by Henke Sass Wolf in Germany and filtered using a 1.2 µm FILTERFLOW® filter extension set.

NOTE: It is recommended that a separate needle and syringe be used to withdrawal the drug product solution from each vial.

Glass bottles are acceptable for belatacept infusions.

The Belatacept solution should then be diluted in D₅W or NSS to a final Belatacept concentration as low as 1 mg/mL. The volume of the fully diluted infusion solution should be approximately 100 mL.

The final Belatacept solution should be visually inspected for particulate matter prior to administration.

The continuous infusion solution must be filtered upon administration using an in-line, sterile, non-pyrogenic, low protein-binding filter with a pore size of 1.2 µm (to be

provided by BMS). This infusion should be administered over a period of approximately 30 minutes. Any unused portion of the infusion solution should not be stored for reuse.

No data are available on the compatibility of Belatacept with other i.v. substances. Other drug substances should not be added or infused simultaneously through the same i.v. line. Assure adequate, appropriate flushing between each drug substance if multiple drugs are administered through the same line sequentially.

10.2 Other Agents

Alemtuzumab will be administered in an inpatient setting and the patient will be monitored with pulse oximetry.. A well-described first dose effect is seen with all anti-lymphocyte preparations though more aggressive cardiopulmonary monitoring is not typically necessary. Additional monitoring can be implemented as deemed necessary by the Principal Investigator in keeping with the standard of care. Belatacept will be administered as an inpatient for doses 1 and 2 and may be given as an outpatient thereafter. Alemtuzumab may be administered via a central venous catheter, a vascular dialysis access, or peripherally and will be administered over a 3 hour period by the nursing or anesthetic staff. Premedication will be given as described above for alemtuzumab prior to drug dosing. Drug will be administered while a member of the attending staff is physically on-site. A member of the attending staff will physically examine the patient prior to the first 2 doses of Belatacept. All patients receiving alemtuzumab or Belatacept will have adequate vascular access to support resuscitative efforts should they be required.

Patients requiring dialysis will be dialyzed prior to receiving alemtuzumab or Belatacept. The transplant pharmacy staff will prepare alemtuzumab and Belatacept within 6 hours of administration. See package insert (alemtuzumab) or Investigators' Brochure (Belatacept) for how drug is supplied and prepared.

No special precautions are warranted in handling alemtuzumab or Belatacept or solutions containing these agents. Empty and partially used ampules or vials should be disposed of according to each institution's standard policies for disposal of biological waste.

Sirolimus will be administered orally initially by the nursing or physician staff, and eventually by the patient in keeping with the package insert.

11 ADVERSE EVENT REPORTING

11.1 Importance of Adverse Event Reporting

Timely and complete reporting of safety information assists in identifying any untoward medical occurrence, thereby allowing: (1) protection of safety of study subjects; (2) a greater understanding of the overall safety profile of the investigational product; (3) recognition of dose-related investigational product toxicity; (4) appropriate modification of study protocols; (5) improvements in study design or procedures; and (6) adherence to worldwide regulatory requirements.

11.2 Data Safety Monitoring Plan

The safety of interventions and treatments associated with this protocol will be under continuous review by the investigative team. A formal Data Safety Monitoring Board will be established to monitor the conduct and progress of the trial and to insure the prompt implementation of patient safeguards. The Board will be assembled including three non-trial affiliated individuals: a nephrologist, a transplant surgeon, and at least one other medical personnel with sufficient knowledge of transplantation to interpret the ongoing progress of the trial. The Principal Investigator will notify the Board of all Serious Adverse Events, and data pertinent to patient recruiting and outcome. The Board will meet annually and convey its recommendations in writing to the Sponsor-investigator and Principal Investigator.. DSMB reports will be submitted to the Institutional Review Board per IRB requirements and meeting minutes will be disseminated to all necessary parties.

All adverse events will be reviewed weekly in a multidisciplinary format that will involve review by a transplant surgeon, a transplant physician, and other members of the transplant staff. All Serious Adverse Events will be reviewed within the accepted guidelines and submitted to the appropriate regulatory bodies governing this study.

Renal failure has many known complications. Pre-existing conditions, which progress in keeping with known history, will not be expeditiously reported. This protocol is not designed to influence those pre existing complications in any way. Therefore, only acute exacerbations that deviate from their natural history will be reported.

11.3 Collection of Safety Information

An *Adverse Event (AE)* is defined as any untoward medical occurrence in a patient or clinical investigation subject administered a pharmaceutical product and that does not necessarily have to have a causal relationship with this treatment. An AE can therefore be any unfavorable and unintended sign (including an abnormal laboratory finding, for example), symptom, or disease temporally associated with the use of a investigational (medicinal) product (IP), whether or not considered related to the IP.

During clinical trials, adverse events can be spontaneously reported or elicited during open-ended questioning, examination, or evaluation of a subject. (In order to prevent reporting bias, subjects should not be questioned regarding the specific occurrence of one or more adverse events.)

Following the subject's written consent to participate in the study, all serious AEs should be collected, including those thought to be associated with clinical trial procedures. The collection of non-serious AE information should begin at initiation of investigational product. Non-serious AE information should also be collected from the start of a placebo lead-in period or other observational period intended to establish a baseline status for the subjects. Following study completion, any SAE thought to be related to study drug or clinical trial procedures should also be reported.

Certain adverse events occur commonly in this study population and will not be recorded as an adverse event, unless it is believed to be associated with the study medications (Alemtuzumab, Sirolimus, Belatacept) and/or it meets the definition of a serious adverse

event. This list is inclusive of, but not limited to events noted below, and will be at the discretion of the Principal Investigator.

Occurrence of:

- Post-op pain.
- Isolated upper respiratory infection, nasopharyngitis, cough, dyspnea and bronchitis.
- Isolated episodes of diarrhea, constipation, nausea, abdominal distention and vomiting.
- Hypokalemia/hyperkalemia, hyponatremia/hypernatremia, hypocalcemia, hypercalcemia, hypophosphatemia/hyperphosphatemia, /hypomagnesemia,/hypermagnesemia, hyperuricemia and hyperglycemia
- Peripheral edema
- Hematuria, proteinuria, glycosuria and dysuria.
- Headache, dizziness, tremor, insomnia, anxiety, fatigue and depression.
- AVF thrombosis and renal artery stenosis.
- Incontinence, hydronephrosis, hematoma, lymphocele, musculoskeletal pain, and atrial fibrillation.
- Acne, facial/body rash, and folliculitis.

Data on concomitant medications will be collected only if they are related to the treatment of a serious adverse or adverse event that is probably, possibly, or definitely related to study medications. All identified AEs must be recorded and described on the appropriate Non-serious or Serious AE page of the CRF. If known, the diagnosis of the underlying illness or disorder should be recorded, rather than its individual symptoms. The following information should be captured for all AEs: date (and time) of onset and resolution, severity of the event (see definitions), Investigator's opinion of the relationship to investigational product (see definitions), treatment required for the AE, cause of the event (if known), and information regarding resolution/outcome. The Investigator shall supply the Sponsor and Ethics Committee with any additional requested information, notably for reported deaths of subjects.

The following categories and definitions of severity should be used:

•

Grading Criteria

The study site will grade the severity of adverse events experienced by the study subjects according to the criteria set forth in the National Cancer Institute's Common Terminology Criteria for Adverse Events Version (CTCAE). This document (referred to herein as the NCI-CTCAE manual) provides a common language to describe levels of severity, to analyze and interpret data, and to articulate the clinical significance of all adverse events

Adverse events will be graded on a scale from 1 to 5 according to the following standards

NCI-CTCAE manual:

- Grade 1 = mild adverse event. (Awareness of event but easily tolerate.)
- Grade 2 = moderate adverse event (Discomfort enough to cause some interferences with usual activity)
- Grade 3 = severe and undesirable adverse event. (Inability to carry out usual activity).
- Grade 4 = life-threatening or disabling adverse event..(Debilitating significantly incapacitates subject despite symptomatic therapy).
- Grade 5 =Death

The following categories and definitions of causal relationship to study drug should be used:

- Certain: There is a reasonable causal relationship between the study drug and the AE. The event responds to withdrawal of study drug (dechallenge), and recurs with rechallenge when clinically feasible.
 - Probable: There is a reasonable causal relationship between the study drug and the AE. The event responds to dechallenge. Rechallenge is not required.
 - Possible: There is reasonable causal relationship between the study drug and the AE. Dechallenge information is lacking or unclear.
 - Not likely: There is a temporal relationship to study drug administration, but there is not a reasonable causal relationship between the study drug and the AE.
 - Not related: There is not a temporal relationship to study drug administration (too early, or late, or study drug not taken), or there is a reasonable causal relationship between another drug, concurrent disease, or circumstance and the AE.
- Adverse Events Related to Study Conditions

If the Investigator believes that an SAE is not related to the investigational product, but is potentially related to the conditions of the study, (such as withdrawal of previous therapy, or complication of a trial procedure), the relationship should be specified in the narrative section of the SAE page of the CRF.

11.4 OverdoseAn overdose is defined as the accidental or intentional ingestion of any dose of a product that is considered both excessive and medically important. For reporting purposes, BMS considers an overdose, regardless of adverse outcome, as an important medical event (see Serious Adverse Events).

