4.2 Analyses

Demographics and Baseline Characteristics

Demographic and baseline characteristics of patients will be summarized descriptively by treatment group, by means and standard deviations (SDs) for continuous variables and frequency distribution for categorical variables. Summaries will be performed based on the data set.

Efficacy Analyses

No formal statistical hypothesis testing will be performed for the primary endpoint. All efficacy analyses will generally be descriptive in nature. The primary efficacy analysis will be to assess the proportion of patients successfully withdrawn from sirolimus for one year. The point estimate of this proportion and the exact two-sided 95% confidence interval (CI) will be provided for each treatment group. A patient will be considered to be successfully withdrawn from immunosuppression for one year if the patient has been administered only belatacept for a period of 365 days, following successful completion of sirolimus, and has not experienced biopsy-proven acute rejection, formation of DSA, or graft loss for this same period of 365 days. Secondary efficacy outcome measures involving incidences and proportions will be descriptively summarized with point estimates and exact, two-sided 95% CIs by treatment group. Other secondary efficacy outcome measures will be descriptively summarized by means and SDs for continuous outcomes and frequency distributions for categorical outcomes.

Safety Analyses

All AEs and SAEs will be summarized by treatment group. Laboratory values will also be descriptively summarized.

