7.6 Immunosuppressive Therapy-specific risks

Alemtuzumab

Alemtuzumab is known to have a significant risk of cytokine release syndrome. This syndrome can usually be minimized by premedication with steroids but can include fever, chills, malaise, hypotension, tachycardia, and pulmonary edema. Lymphopenia may be associated with increased risk of infection.

Sirolimus

Phase III studies of sirolimus in cyclosporine based regimens have revealed mild dose related thrombocytopenia and increases of serum triglycerides and cholesterol. This latter finding is probably its most consistent effect and was seen in 40-50% of patients. Hypertriglyceridemia predominates. HMG-CoA reductase inhibitors and fibric acid have been used and well tolerated to counteract the hyperlipidemia associated with sirolimus. Additionally, the unexpected finding of nephrotoxicity has been encountered but is likely attributable to sirolimus' potentiation of CNI nephrotoxicity and thus is likely to be inapplicable in this trial. Other common events reported in trials include leukopenia, hypertension, anemia, nausea, vomiting, elevated liver enzymes, rash and acne [37,38] Other risks from the package insert for sirolimus include possible development of lymphoma and other malignancies, particularly of the skin, increased susceptibility to infection including opportunistic infections, fatal infections, and sepsis, and lymphocele, a known surgical complication of renal transplantation, occurring significantly more often in a dose-related fashion in sirolimus-treated patients.

Belatacept in Kidney Transplant Study

Specific risks associated with belatacept may include those typically associated with transplant related immunosuppression including infection and malignancy.

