Transplant rejection was reported more commonly with both doses of belatacept than with CsA. Subsequent evaluation revealed that these reports reflected episodes of suspected acute rejection later disproven by central biopsy, as well as episodes that resolved spontaneously without treatment. All reported AEs of transplant rejection that were subsequently confirmed by biopsy have been counted in the efficacy summaries provided above. AEs commonly observed during CsA treatment, such as anemia, leukopenia, hirsutism, tremor, hypomagnesemia, and hypertension, were reported less frequently with belatacept than with CsA in this study. Infectious complications occurred with comparable frequency. Pulmonary edema and proteinuria were reported more frequently with belatacept than with CsA. The significance of these events requires further evaluation.

Serious Adverse Events

The most frequent SAEs are summarized by MedDRA system organ class and preferred term in Table 1.3.4.4C. As noted above, SAEs were reported somewhat more frequently in the belatacept treatment groups than in the CsA group. This difference is accounted for by an increased frequency of reporting acute rejection as an AE in the belatacept groups. Subsequent evaluation revealed that these reports reflected episodes of suspected rejection later disproven by central biopsy, as well as episodes that resolved spontaneously without treatment. All reported AEs of transplant rejection that were subsequently confirmed by biopsy have been counted in the efficacy summaries provided above in Section 1.1.4.3.

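### Non-serious events that the protocol itself links to sirolimus or belatacept are recorded only if the investigator attributes them to a study drug, so their all-causality rates can be understated

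*Combined protocol and SAP*

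**What the plan says.** Section 11.3 first defines an adverse event without regard to causality. It then carves out events that are common in this population: such an event "will not be recorded as an adverse event, unless it is believed to be associated with the study medications", with alemtuzumab, sirolimus and belatacept named, "and/or it meets the definition of a serious adverse" event. The same section says that from consent "all serious AEs should be collected, including those thought to be associated with clinical trial procedures".

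The list covers, among others, isolated respiratory and gastrointestinal complaints, peripheral edema, proteinuria, headache, acne and rash, and the line "Incontinence, hydronephrosis, hematoma, lymphocele, musculoskeletal pain, and atrial fibrillation". It is not closed: "This list is inclusive of, but not limited to events noted below, and will be at the discretion of the Principal Investigator".

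Section 7.6 reports lymphocele as "occurring significantly more often in a dose-related fashion in sirolimus-treated patients". Appendix C says of the earlier kidney transplant study of belatacept (IM103100): "Pulmonary edema and proteinuria were reported more frequently with belatacept than with CsA", and adds that these findings need further evaluation.

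On analysis, Section 4.2 says only: "All AEs and SAEs will be summarized by treatment group". It does not mention that some events are filtered before they reach the database.

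**The concern.** A relatedness judgement normally sits beside an event that has already been recorded. Here, for listed non-serious events, it decides whether the event is recorded at all. The judgement is made in an open-label, non-randomized study (Section 3.1), so no comparison arm passes through the same filter. The filter can only lower the observed all-causality rate.

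This matters most for events with both a background cause and a drug contribution. Section 7.6 describes lymphocele as a recognised surgical complication and also as more frequent with sirolimus. In one patient the operation is a ready explanation, and the causality categories in Section 11.3 allow a rating of not related when another circumstance reasonably explains the event. A drug-related excess would show only in the all-causality rate, which is the quantity not collected.

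There is little to rebuild the data from afterwards. Concomitant medication is collected only for serious or drug-related events (Sections 6.5 and 11.3). The safety board is told of serious events and of recruitment and outcome data (Section 11.2). Since the case for the regimen includes fewer side effects than conventional therapy, tolerability rates are part of what the trial will be read for.

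**Working it through.** The plan gives no figure for this rule, so there is none to reproduce. The check is a comparison of passages, followed by an illustration of scale.

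**1. The Section 11.3 list against effects named elsewhere**

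- Sirolimus, Section 7.6: nausea, vomiting, rash, acne and lymphocele are named and are on the list. Leukopenia, anemia, hypertension, liver enzymes, thrombocytopenia and lipids are named and are not on it.
- Belatacept, Section 7.6 (side effects most often reported): diarrhea, constipation, nausea, swelling and cough are on the list. Urinary tract infection, fever, high blood pressure and low white cells are not.
- Belatacept, Appendix C: proteinuria is on the list.
- First cohort, Section 1.3.5: four of 20 patients were converted from sirolimus for arthralgias, edema or mouth ulcers. Edema is on the list, arthralgia is covered if musculoskeletal pain is read to include it, and mouth ulcers are not on it.
- Section 9.3: headache is a neurologic symptom to be reviewed, and it is on the list.

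Counting nausea once, ten effects named in Section 7.6 or Appendix C are on the list: nausea, vomiting, rash, acne, lymphocele, diarrhea, constipation, swelling/edema, cough and proteinuria.

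**2. Internal consistency**

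- Section 11.3 defines adverse events irrespective of cause and later requires all identified adverse events to be recorded. Between these two statements it exempts the listed ones.
- Section 11.8 repeats the exemption for laboratory abnormalities that need corrective treatment.
- Section 11.9 points the other way: clinically significant changes on examination or other safety assessment go on an adverse event page. A clinically significant rash or edema found on examination and judged unrelated falls under both rules.
- Section 4.2 describes the output as all adverse events.

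**3. Illustration of scale**

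Let p be the true rate of a listed non-serious event and q the share of cases the investigator attributes to a study drug. Then:

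- recorded rate = p × q
- expected recorded cases in n patients = n × p × q
- chance of no recorded case = (1 − p × q)^n

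Inputs: p from the more intensive belatacept arm of IM103100 (Appendix C, N = 74): diarrhea 17/74 = 23.0%, nausea 19/74 = 25.7%, peripheral edema 23/74 = 31.1%. n = 20 from Section 3.1. q is an assumption, because the documents give no value. All cases are treated as non-serious, and the restriction of the gastrointestinal item to isolated episodes is ignored.

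| Event | q = 0.25 | q = 0.50 | q = 0.75 | q = 1 |
|---|---|---|---|---|
| Diarrhea | 5.7% | 11.5% | 17.2% | 23.0% |
| Nausea | 6.4% | 12.8% | 19.3% | 25.7% |
| Peripheral edema | 7.8% | 15.5% | 23.3% | 31.1% |

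For diarrhea, expected recorded cases in 20 patients are 20 × 0.230 = 4.6 with full recording and 20 × 0.230 × 0.25 = 1.1 at q = 0.25. The chance of no recorded case is (1 − 0.230)^20 = 0.5% with full recording and (1 − 0.057)^20 = 31% at q = 0.25. At q = 1 the filter has no effect.

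**The case against.** The strongest objection is that the rule is narrower than it looks. Serious events bypass it whatever their cause, and all of them are collected from consent. Many known toxicities are not on the list. The respiratory and gastrointestinal items begin with a restriction to isolated occurrences. Known drug effects are also the events an investigator is most likely to attribute to a drug: a rating of possible does not require dechallenge information, and events leading to conversion from sirolimus would presumably be attributed to it. Section 9.3 schedules neurologic assessments every three months to year 2 and every six months after that. Section 11.9 recovers some examination findings, and Section 4.2 summarizes laboratory values separately. No planned external comparison in Section 2.2 uses rates of nonspecific events such as acne or headache. Finally, some listed events were about as common on cyclosporine in IM103100 (peripheral edema 29.6%, against 31.1% and 28.2% on belatacept), which supports the protocol's view that they are background events.

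Most of this stands and limits the point. It does not remove it. Isolated does not qualify lymphocele, rash, acne, edema, proteinuria or headache, and the Principal Investigator may extend the list. A high background rate makes attribution in a single patient less reliable, which is a reason to record first and attribute second.

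A reader might infer from IM103100 that the filter removes about 40 percentage points, since 73/74 = 98.6% of the more intensive arm had any adverse event and 43/74 = 58.1% had a related one. The documents do not support that. The difference is per patient, covers all event types including serious and unlisted ones, and comes from patients on basiliximab, mycophenolate and steroids. It shows that a relatedness filter can matter and does not estimate q for the listed events. Nor should a reader conclude that neurologic warning signs in general go unrecorded: memory and personality change are in Section 9.3 but not on the Section 11.3 list.

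**Conclusion.** The point holds for non-serious events on the Section 11.3 list. The protocol makes their recording conditional on an unblinded attribution, includes at least ten effects it names itself for sirolimus or belatacept, and then promises a summary of all adverse events. The all-causality rates of those events can be understated. It does not follow that they will be, because the bias is zero if every case is attributed to a study drug.

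It would go too far to say that adverse event rates in general are understated. Serious event rates, unlisted events and the primary endpoint are untouched. The size cannot be derived from the documents; the table rests on an assumed q and on event rates borrowed from a different background regimen. This is a modest defect in safety data collection, worth correcting because the correction is cheap.

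**What to change.** Remove from the Section 11.3 list every event the protocol names as a sirolimus or belatacept effect: nausea, vomiting, diarrhea, constipation, cough, peripheral edema, rash, acne, lymphocele, proteinuria, and musculoskeletal pain so far as it covers arthralgia. Remove headache as well, because Section 9.3 treats it as a symptom to review. Record these events whatever the attributed cause and use the relatedness field already on the case report form, so that both all-causality and related rates can be tabulated.

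The rest of the list can stay. Align Sections 11.8 and 11.9 with it, so that a site has one rule for treated laboratory abnormalities and for clinically significant examination findings. State in Section 4.2 that adverse event tables exclude the remaining listed non-serious events judged unrelated.

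The cost is additional adverse event entries for 20 to 40 patients (Section 3.1 gives 20, the synopsis about 40). No new visits are needed.
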